8.41 Criteria for starting treatment with Cmab or Pmab

Event	Criteria for starting treatment with Cmab / Pmab
Skin symptom (rash acneiform, dry skin, paronychia, etc.)	Grade 2 or lower (Local infection is considered grade 3 if oral antimicrobial treatment is required, but not if oral antibiotic treatment is given based on the anti-inflammatory effect.)
Infusion-related reaction	Grade 1 or lower
Other	At the discretion of the treating physician, treatment can be delayed due to an adverse event not listed above if necessary.

8.42 Criteria for starting treatment with irinotecan

Event	Criteria for starting treatment with irinotecan
Neutrophil count	$\geq 1200/\text{mm}^3$
Platelet count	$\geq 7.5 \times 10^4/\text{mm}^3$
AST, ALT	\leq upper limit of normal x 3 (\leq upper limit of normal x 5 in subjects with liver metastasis)
T-bil	\leq upper limit of normal x 1.5
Pyrexia	Absence of pyrexia ($\geq 38^\circ\text{C}$)
Diarrhea, oral mucositis	Grade 1 or lower
Other	At the discretion of the treating physician, treatment can be delayed due to an adverse event not listed above if necessary.

8.43 Criteria for changing the dose level at the second and subsequent doses for Cmab or Pmab and Irinotecan

If any of the events listed below occurs after the previous dose, the next dose will be reduced or discontinued. Dose reduction will be performed one level at a time. When treatment with irinotecan is discontinued in accordance with the criteria for dose reduction/discontinuation during combination therapy with Cmab/Pmab and irinotecan, treatment with Cmab/Pmab will be continued as protocol treatment if none of the criteria for discontinuing protocol treatment are met. Treatment with irinotecan alone should not be continued. The dose should not be increased once reduced.

8.431 Criteria for changing the dose level of Cmab or Pmab at the second and subsequent doses and the dose level

Event	Cmab \ Pmab
1st episode of grade 3 or higher skin symptom	No dose reduction
2nd and subsequent episodes of grade 3 or higher skin symptom	1-level dose reduction
The treating physician concludes that the dose should be reduced due to an adverse event not listed above.	1-level dose reduction

8.432 Criteria for changing the dose level of irinotecan at the second and subsequent doses and the dose level

Event	Grade	Irinotecan
Neutropenia, thrombocytopenia	4	1-level dose reduction
Grade 3 neutropenia or grade 3 thrombocytopenia for more than 7 days	3	
Febrile neutropenia, infection, nausea, vomiting, diarrhea, fatigue, oral mucositis	3	
The treating physician concludes that the dose should be reduced due to an adverse event not listed above. (Specify the reason on the case report form.)	3	

Irinotecan should be discontinued if dose reduction is necessary more than -2 level.

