7.0 Protocol Treatment

Drugs will be administered in accordance with the information on the respective package inserts. Treatment will be given according to the schedule specified in the protocol. The terms “delay,” “modification,” and “omission” are defined as follows:

Delay: A delay indicates dose was postponed or not received when expected.

Modification: Indicates a change in dose level during the current cycle. However, if a modification was issued after the last dose was received in the current cycle, the modification should be reported on the subsequent cycle.

Omission: Indicates a dose was skipped and not made up, or that the drug was discontinued.

Arm A, treatment with regorafenib followed by anti-EGFR therapy (\pm irinotecan).

Arm B, treatment with anti-EGFR therapy (\pm irinotecan) followed by regorafenib.

Treatment on regorafenib will be continued in accordance with Section 7.11 “Planned treatment with regorafenib” until any of the “Criteria for discontinuing treatment with regorafenib” (Section 8.34) is met.

Treatment on Anti-EGFR therapy (\pm irinotecan) will be continued in accordance with Section 8.4, “Combination therapy of Anti-EGFR therapy (cetuximab (Cmab) **OR** panitumumab (Pmab) and irinotecan” until any of the “Criteria for discontinuing treatment including Cmab or Pmab” (Section 8.44) is met.

Patients assigned to Anti-EGFR therapy will receive either cetuximab or panitumumab per treating physician discretion and will be dosed per prescribing guidelines. Patients cannot switch between cetuximab and panitumumab during the course of the study. The use of irinotecan is per treating physician discretion and will be dosed per prescribing guidelines. If treating physician chooses to add irinotecan, irinotecan must be included in treatment starting at cycle 1.

7.1 Treatment Schedule - Use actual weight or estimated dry weight if fluid retention

Agent	Dose	Route	Frequency	ReRx
Regorafenib	80mg daily (Starting dose) See table 7.11	PO	Daily for Days 1-21 of 28 day cycle	Every 28 days
Cetuximab*	500mg/m ²	IV	Days 1, 15	Every 28 days
Panitumumab*	6mg/kg	IV	Days 1, 15	Every 28 Days
Irinotecan	180mg/m ²	IV	Days 1, 15	Every 28 days

* Patients assigned to Anti-EGFR therapy will receive **EITHER** cetuximab **OR** panitumumab, not both

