8.0 Dosage Modification Based on Adverse Events

Strictly follow the modifications in the following tables for the first **two** cycles, until individual treatment tolerance can be ascertained. Thereafter, these modifications should be regarded as guidelines to produce mild-to-moderate, but not debilitating, side effects. If multiple adverse events are seen, administer dose based on greatest reduction required for any single adverse event observed. Reductions or increases apply to treatment given in the preceding cycle and are based on adverse events observed since the prior dose.

ALERT: *ADR reporting may be required for some adverse events (See Section 10)*

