8.44 Criteria for discontinuing treatment including Cmab or Pmab

Treatment with Cmab/Pmab plus irinotecan or Cmab/Pmab alone will be discontinued if any of the criteria for discontinuation listed below is met. When treatment with irinotecan is discontinued due to an irinotecan-related adverse event, treatment with Cmab/Pmab alone will be continued if none of the following criteria are met:

1. When treatment including Cmab/Pmab is considered to be ineffective
 - Radiographically confirmed disease progression per RECIST 1.1.
 - Significant worsening of symptoms or physical findings (disease progression should be radiographically confirmed wherever possible).
2. When treatment with Cmab/Pmab cannot be continued
 - It is necessary to reduce the dose of Cmab/Pmab to less than dose level -3 according to the criteria for dose reduction/modification of treatment.
 - Treatment cannot be resumed within 28 days after modification of treatment due to an adverse event.
 - The 3rd episode of grade 3 skin toxicity occurs despite symptomatic treatment and dose reduction of Cmab/Pmab.
 - Grade 3 or higher infusion-related reaction related to Cmab/Pmab.
 - Grade 4 non-hematological toxicity.
 - The treating physician concludes that treatment with Cmab/Pmab cannot be continued due to safety concerns.
3. Patient's request for discontinuation of treatment with Cmab/Pmab.
4. After entry, the patient is found to be ineligible for the study, and it is concluded that further treatment including Cmab/Pmab is detrimental to him/her.
5. Transfer to another hospital for any reason during treatment including Cmab/Pmab.

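### Table 8.431 directs re-dosing after grade 4 skin events, and after some third or later grade 3 skin episodes, where the controlling stop list in 8.44 discontinues anti-EGFR therapy

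*Combined protocol and SAP*

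**What the plan says.** Section 8.43 introduces the dose-change tables for the second and later doses: "If any of the events listed below occurs after the previous dose, the next dose will be reduced or discontinued". Table 8.431, beneath it, has two skin rows for cetuximab and panitumumab:

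- "1st episode of grade 3 or higher skin symptom": the dose is not reduced.
- "2nd and subsequent episodes of grade 3 or higher skin symptom": the dose goes down one level.

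A third row lets the physician reduce one level for an unlisted adverse event. No row says discontinue.

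Section 8.44 lists the criteria for stopping anti-EGFR treatment, and any one of them is enough. Three matter here:

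- "Grade 4 non-hematological toxicity", with no exception for skin.
- "The 3rd episode of grade 3 skin toxicity occurs despite symptomatic treatment and dose reduction of Cmab/Pmab".
- "Treatment cannot be resumed within 28 days after modification of treatment due to an adverse event".

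Three other places set how these are used. Section 7.0 says anti-EGFR therapy "will be continued in accordance with Section 8.4" until an 8.44 criterion is met. Section 8.0 opens with "Strictly follow the modifications in the following tables for the first" two cycles, after which the tables become guidelines. Section 8.41 allows a dose once skin symptoms are grade 2 or lower, whatever the earlier peak grade.

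**The concern.** A site that looks up a skin event in Table 8.431 gets a definite answer for every grade from 3 upward and every episode number. For some of those combinations 8.44 requires the opposite. The consequence is re-exposure to the causative drug, at full dose after a first grade 4 skin event, in a patient who should have stopped. Section 15.37 notes that panitumumab carries a boxed dermatologic warning. Section 1.3 says acneiform rash usually appears 1 to 3 weeks after administration, so early events fall within the two cycles in which Section 8.0 asks for strict use of the tables. In Arm B the stop is also the point at which the patient may move to regorafenib: Section 6.4 requires re-registration within 28 days of documented progression or intolerance.

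**Working it through.** **Step 1. Compare the two sections for each grade and episode.** The plan states no figure to reproduce; the check is a comparison of text.

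| Skin event | Table 8.431 | Section 8.44 | Result |
|---|---|---|---|
| Grade 3, episode 1 | same dose | no stop | agree |
| Grade 3, episode 2 | one level down | no stop | agree |
| Grade 3, episode 3 or later | one level down | stop, if despite symptomatic treatment and dose reduction | conflict when the condition is met |
| Grade 4, first episode | same dose | stop | conflict |
| Grade 4, later episode | one level down | stop | conflict |

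In the third line, a patient managed by the table has already been reduced at episode 2. The dose-reduction half of the 8.44 condition is therefore met by episode 3. Whether symptomatic treatment was given depends on the patient.

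**Step 2. Doses on each reading** (starting doses and levels from 7.1 and 7.21; doses on days 1 and 15 of a 28-day cycle).

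*Grade 4 event after dose 1.* Under Table 8.431, dose 2 is the full cetuximab 500 mg/m² or panitumumab 6 mg/kg once the skin is grade 2 or lower. If the 28-day limit is counted from the scheduled day 15 dose (an assumption), recovery by day 15 + 28 = 43 is soon enough. Under 8.44 there is no dose 2.

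*Fastest grade 3 path.* This is an extreme: one episode after each of doses 1, 2 and 3, with recovery in time for every scheduled dose (days 1, 15, 29, 43).

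- Cetuximab: 500, 500, 400, 300 mg/m². Dose 4 is 300/500 = 60% of the start.
- Panitumumab: 6, 6, 4.8, 3.6 mg/kg. Dose 4 is 3.6/6 = 60% of the start.
- Under 8.44: no dose 4 if the third episode occurred despite symptomatic treatment, since the dose was already reduced.

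**Step 3. How many patients.** Inputs: total expected accrual 72 (16.22); grade 3 or higher skin toxicity 9.4% to 16.7% with cetuximab (1.3). The documents give no such rate for panitumumab.

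- 72 × 0.094 = 6.8
- 72 × 0.167 = 12.0

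This assumes that all 72 receive an anti-EGFR antibody, which is an upper bound, and that the cetuximab rate applies to both drugs. The documents give no rate for grade 4 skin events or for third grade 3 episodes. Purely as an illustration, if 5% to 25% of those patients reached one:

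- 6.768 × 0.05 = 0.3
- 12.024 × 0.25 = 3.0

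The 5% to 25% share is an assumption without a source.

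**Step 4. Compare with neighbouring tables.** Table 8.22b stops at the third grade 3 hand-foot episode and Table 8.23 stops at grade 4 hypertension. Both match the regorafenib stop list in 8.3. Table 8.432 lists its non-hematological irinotecan events at grade 3 only. Table 8.21 is not a model: its grade 4 row allows a one-level reduction and leaves stopping to discretion, while 8.3 stops other grade 4 non-hematological toxicity.

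**The case against.** The best reply is that the protocol already settles the matter. Section 7.0 makes 8.44 the limit on treatment, 8.44 is mandatory, and it directly follows the 8.43 tables. Section 8.43 concerns dose level and 8.44 concerns who stops, so a grade 4 patient should never reach the dose question. The lead-in to 8.43 also mentions discontinuation. Nor is the table self-contained: the stop for severe infusion reactions and the 28-day limit appear only in 8.44.

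The precedence argument stands, which is why this is an inconsistency and not a missing rule. But silence and contradiction differ. On infusion reactions the table sends the reader elsewhere; on grade 4 skin events it gives an answer, and the answer is wrong. The 28-day limit and the physician's safety stop lower the risk, but they do not settle what happens to a patient who recovers in time.

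Four further objections limit the point:

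- A reader might infer that 8.44 stops every third grade 3 skin episode. It does not; the episode must occur despite symptomatic treatment and dose reduction. Where symptomatic treatment was not given, the one-level reduction does not conflict with that criterion.
- A reader might take the strict-use instruction in 8.0 to put the tables above 8.44. Nothing there says so. It covers two cycles, or four anti-EGFR doses, and only the fastest path above puts a third episode and a further dose inside that window. It adds weight to the grade 4 conflict and little to the other.
- Section 7.0 also requires dosing according to the package inserts. Their content is not in the documents, so it can neither resolve the conflict nor show how serious it is.
- The base of 72 is generous. Arm A patients reach anti-EGFR therapy only if re-registered, at the physician's discretion (13.5 and 13.6), and 12 of the 72 are left-sided patients enrolled before Amendment 2.

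**Conclusion.** Table 8.431 is wrong as written on a matter of patient safety. The main conflict is grade 4 skin events at any episode: the table re-doses, 8.44 stops. The secondary conflict is a third or later grade 3 episode that meets the 8.44 condition.

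A reader might infer that the protocol has no stop rule for severe skin toxicity. It has one in 8.44, and Section 7.0 gives it control. Nor is there a threat to the primary result. OS runs from randomization to death from any cause, patients are followed for survival after protocol treatment ends, and the one-sided 0.1 level and 80% power do not depend on this table. Any effect on PFS censoring is negligible.

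Few patients would be affected. The 6.8 to 12.0 with any grade 3 or higher skin toxicity is an upper-bound pool built on a cetuximab rate. How many of them would meet a conflicting row is unknown, and the 0.3 to 3.0 illustration rests on an assumed share. The case for correcting the table is that it can direct treatment of a patient who must stop, and that correction is nearly free.

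**What to change.** Reword the skin rows of Table 8.431 as follows:

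- Grade 3, first episode: no dose reduction.
- Grade 3, second episode: reduce one level.
- Grade 3, third or later episode: discontinue if it occurs despite symptomatic treatment and dose reduction (8.44); otherwise reduce one level.
- Grade 4 skin event, any episode: discontinue (8.44).

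The conditional third row keeps an instruction for the episode that 8.44 does not stop. Two rows are reworded and two added. The change brings the table into line with the existing stop list and has no effect on sample size, alpha, power or timelines. The similar grade 4 mismatch between Table 8.21 and 8.3 could be corrected in the same amendment.

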8.44 Criteria for discontinuing treatment including Cmab or Pmab

Treatment with Cmab/Pmab plus irinotecan or Cmab/Pmab alone will be discontinued if any of the criteria for discontinuation listed below is met. When treatment with irinotecan is discontinued due to an irinotecan-related adverse event, treatment with Cmab/Pmab alone will be continued if none of the following criteria are met:

1. When treatment including Cmab/Pmab is considered to be ineffective
 - Radiographically confirmed disease progression per RECIST 1.1.
 - Significant worsening of symptoms or physical findings (disease progression should be radiographically confirmed wherever possible).
2. When treatment with Cmab/Pmab cannot be continued
 - It is necessary to reduce the dose of Cmab/Pmab to less than dose level -3 according to the criteria for dose reduction/modification of treatment.
 - Treatment cannot be resumed within 28 days after modification of treatment due to an adverse event.
 - The 3rd episode of grade 3 skin toxicity occurs despite symptomatic treatment and dose reduction of Cmab/Pmab.
 - Grade 3 or higher infusion-related reaction related to Cmab/Pmab.
 - Grade 4 non-hematological toxicity.
 - The treating physician concludes that treatment with Cmab/Pmab cannot be continued due to safety concerns.
3. Patient's request for discontinuation of treatment with Cmab/Pmab.
4. After entry, the patient is found to be ineligible for the study, and it is concluded that further treatment including Cmab/Pmab is detrimental to him/her.
5. Transfer to another hospital for any reason during treatment including Cmab/Pmab.

8.5 Management of neutropenia, leukopenia and thrombocytopenia

Adverse event of neutropenia and leukopenia should be managed as deemed appropriate by the treating physician with close follow up and modification of study drug if required.

Primary prophylaxis with Granulocyte colony-stimulating factor (G-CSF) is not recommended, however, if a patient develops febrile neutropenia, study treatment should be stopped and appropriate management including G-CSF should be given according to local hospital guidelines. Please note that G-CSF should not be used within at least 24 h (7 days for PEGylated G-CSF) of the last dose of study treatment unless absolutely necessary. Platelet transfusions, if indicated, should be done according to local hospital guidelines. Study treatment can be interrupted for CTCAE grade 1 /2 neutropenia or thrombocytopenia as per treating physician's judgement. In case of CTCAE grade 3/4 neutropenia, leukopenia or thrombocytopenia, study treatment should be interrupted for a maximum of 4 weeks. Study treatment can be restarted at the same dose if an adverse event of neutropenia, leukopenia or thrombocytopenia has been recovered up to CTCAE grade 1 or less.

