15.192 Late diarrhea (generally occurring more than 24 hours after administration of CAMPTOSAR) can be life threatening since it may be prolonged and may lead to dehydration, electrolyte imbalance, or sepsis.

- 15.193 Hypersensitivity reactions including severe anaphylactic or anaphylactoid reactions have been observed. Discontinue CAMPTOSAR if anaphylactic reaction occurs.
- 15.194 Interstitial Pulmonary Disease (IPD)-like events, including fatalities, have occurred in patients receiving irinotecan (in combination and as monotherapy). Risk factors include pre-existing lung disease, use of pneumotoxic drugs, radiation therapy, and colony stimulating factors. Patients with risk factors should be closely monitored for respiratory symptoms before and during CAMPTOSAR therapy.
- 15.195 Hold CAMPTOSAR if neutropenic fever occurs or if the absolute neutrophil count drops
- 15.196 Patients should be warned about the potential for dizziness or visual disturbances which may occur within 24 hours following the administration of CAMPTOSAR.

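### Febrile neutropenia: section 8.5 stops study treatment without naming a drug or a duration, and neither a permanent nor a temporary reading squares with the other sections

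*Combined protocol and SAP*

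**What the plan says.** All references are to the combined protocol and SAP.

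- **8.5** (management of neutropenia, leukopenia and thrombocytopenia): "if a patient develops febrile neutropenia, study treatment should be stopped and appropriate management including G-CSF should be given". No drug, duration or grade is given. For grade 3/4 cytopenia the same paragraph says "study treatment should be interrupted for a maximum of 4 weeks". It then adds: "Study treatment can be restarted at the same dose if an adverse event of neutropenia, leukopenia or thrombocytopenia has been recovered", the required recovery being to grade 1 or less.
- **8.43 and table 8.432** (irinotecan dose changes): the lead-in reads "If any of the events listed below occurs after the previous dose, the next dose will be reduced or discontinued". The grade 3 row "Febrile neutropenia, infection, nausea, vomiting, diarrhea, fatigue, oral mucositis" falls under the action "1-level dose reduction". That action is printed once, on the first row, and I read it as a merged cell covering the rows below.
- **15.195 in the irinotecan nursing guidelines**: "Hold CAMPTOSAR if neutropenic fever occurs or if the absolute neutrophil count drops". The sentence breaks off there in the text available, which I do not count as a fault. The number 15.195 is used twice; the regorafenib item with that number concerns gastrointestinal effects.
- **8.4**: when the antibody's start criteria are met but irinotecan's are not, the antibody can be given alone.
- **8.41 and 8.431** (antibody start and dose criteria): neither names neutropenia or febrile neutropenia, though both leave room for physician judgement on unlisted events.
- **8.44** (ending anti-EGFR treatment): febrile neutropenia is not listed. The grade 4 criterion covers non-hematological toxicity only. Failure to resume within 28 days of a modification for an adverse event is listed.

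**The concern.** Febrile neutropenia is a serious event, and sites need one instruction for it. On anti-EGFR therapy plus irinotecan, a site following 8.5 stops the antibody as well as irinotecan. A site following 8.4 and 8.432 can give the antibody and lower irinotecan one level. The two sites also lack a common answer on whether treatment resumes and at what irinotecan dose.

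At stake is the consistency of treatment received. On one reading of 8.5, the censoring of progression-based secondary endpoints is also affected. Anti-EGFR therapy is initial treatment in Arm B and sequential treatment in Arm A, so the endpoints touched would differ by arm.

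**Working it through.** No figure in the plan depends on this point, so the main check is a comparison of the rules for one event: febrile neutropenia during anti-EGFR therapy plus irinotecan.

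| Section | Drugs reached | Action | What follows |
|---|---|---|---|
| 8.5 | All study treatment | Stop | Not stated for this event; same-dose restart allowed after recovery from neutropenia |
| 8.432 | Irinotecan | Next dose one level lower | 8.43 bars raising a reduced dose again |
| 15.195 (irinotecan) | Irinotecan | Hold | Not stated |
| 8.4 | Antibody | May be given alone if irinotecan criteria fail | Continues |
| 8.44 | Antibody with or without irinotecan | Event not listed | Ends only if another criterion is met |

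**Scope.** 8.5 reaches both drugs. 8.432 and 15.195 reach irinotecan only. Holding irinotecan now and lowering its next dose can both be done, so 15.195 and 8.432 agree; 15.195 adds only to the scope conflict with 8.5.

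**If the stop is permanent.** There is no next irinotecan dose to reduce, which contradicts 8.432. Anti-EGFR treatment would also end for a reason absent from 8.44.

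**If the stop is temporary.** The only restart rule in 8.5 allows the same dose after neutropenia has recovered. 8.43 with 8.432 requires one level less. If the restart sentence is held not to cover febrile neutropenia, the dose conflict goes. 8.5 then gives no restart rule for the event, and the scope conflict remains.

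**Precedence.** 8.0 makes the tables strict for the first two cycles and guidelines after that. Its greatest-reduction rule covers several adverse events, not several rules for one event. Section 7.0 defines delay, modification and omission, but not the terms that 8.5 and 15.195 use.

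**Endpoints.** The patient leaves the anti-EGFR phase only if the stop is read as permanent or runs past the 28 days in 8.44.

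- Arm B: the patient may move to regorafenib (6.41, 13.6). Without progression or death, PFS1 is censored at the last assessment before sequential treatment (16.321).
- Arm A: protocol treatment ends. Without progression or death, PFS2 and stPFS are censored at the last assessment on sequential treatment (16.322, 16.323).
- OS runs from randomization to death from any cause (16.11), so its definition and censoring do not change.

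**Number of patients.** Inputs: 52 evaluable patients (16.22); neutropenic fever in the 1-10% class for irinotecan (15.47); irinotecan use of 50% to 100%, which is my assumption because the plan gives no figure.

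Expected events = patients × share on irinotecan × event rate.

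- Low: 52 × 0.5 × 0.01 = 0.26, about 0.3.
- High: 52 × 1.0 × 0.10 = 5.2.

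Both figures assume that all 52 patients start anti-EGFR therapy. Arm A patients do so only after regorafenib and an optional re-registration (13.5, 13.6), so the true count is lower.

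**The case against.** The strongest reply is that the passages can be followed in sequence: stop during the acute event (8.5), hold irinotecan (15.195) until the 8.42 criteria on neutrophils and fever are met, then give the next irinotecan dose one level lower (8.432). On this view 8.41 lets the physician delay the antibody, 8.4 only permits giving it alone, and 8.5 itself opens by leaving management to the treating physician.

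Much of this stands, and it rules out several stronger readings that a reader might infer:

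- *That 8.5 takes every such patient off the anti-EGFR phase.* The contrast with the interruption wording in the same paragraph invites this. But elsewhere the protocol states permanence outright (table 8.21 footnote c, table 8.22b), and neither 8.44 nor 8.6 names the event. 8.5 does not say the stop is permanent.
- *That there are three rival rules.* 15.195 and 8.432 are compatible.
- *That 8.43 expressly continues the antibody here.* That sentence covers irinotecan being discontinued, not reduced. Continuation after a reduction is inferred from 8.4, 8.431 and 8.44.
- *That switching would be undefined.* 6.41 allows re-registration for intolerance, and 13.6 covers leaving initial treatment for reasons other than progression.

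The reply does not remove the problem. The sequence works only if a site treats the 8.5 stop as temporary, sets aside the same-dose restart for this event, and decides for itself when the antibody resumes. The protocol says none of these things.

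**Conclusion.** The text is wrong as written. For febrile neutropenia on anti-EGFR therapy plus irinotecan, 8.5 conflicts with the irinotecan-only rules on which drugs are affected. It also conflicts with 8.432 and 8.44 if the stop is permanent, or with 8.432 on the restart dose if it is temporary and the restart sentence applies. This rests on reading the 8.432 action as a merged cell.

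The statistical effect is small and conditional. At most 0.3 to 5.2 of 52 patients would have the event, given the assumed irinotecan use and the general drug-information class, which is not a rate for this regimen. Only those whose stop is taken as permanent, or exceeds 28 days, would leave the phase, with PFS1 censored in Arm B, or PFS2 and stPFS in Arm A, if no event has occurred. A reader might infer a threat to the primary comparison through censoring; the OS definition does not support that. The case for change is mainly consistent handling of a serious safety event.

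**What to change.** Reconcile 8.5, 8.4, 8.432, 8.44 and the irinotecan 15.195 so that one passage states, for febrile neutropenia:

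1. which drugs the action applies to;
2. whether it is temporary or permanent;
3. which dose rule governs any restart.

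The other passages should refer to that one. Which rule applies is for the sponsor to decide, and no view is offered here. The cost is protocol wording only, with no change to sample size, endpoints or analysis.

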7.22 Dose levels of irinotecan

Dose reduction level	Dose of irinotecan
Initial dose level	180 mg/m ²
-1	150 mg/m ²
-2	120 mg/m ²
-3	100 mg/m ²

- 7.3 Study treatment with regorafenib, cetuximab, panitumumab, and Irinotecan may be administered up to 3 days before or after the scheduled Day 1, Day 15 of each cycle due to administrative reasons.

NOTE: Future treatment dates may need to be adjusted as a result of the ±3 days.

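### Section 8.5 lets irinotecan restart at an unchanged dose after recovered grade 4 neutropenia or thrombocytopenia, where 8.43 and 8.432 give a one-level reduction

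*Combined protocol and SAP*

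**What the plan says.** Section 8.5 covers all study drugs together: "In case of CTCAE grade 3/4 neutropenia, leukopenia or thrombocytopenia, study treatment should be interrupted for a maximum of 4 weeks". It continues: "Study treatment can be restarted at the same dose if an adverse event of neutropenia, leukopenia or thrombocytopenia has been recovered", and the sentence ends by setting recovery at CTCAE grade 1 or less. It makes no exception for irinotecan or for grade 4 events.

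Section 7.3 shows that the term includes irinotecan: "Study treatment with regorafenib, cetuximab, panitumumab, and Irinotecan may be administered up to 3 days before or after the scheduled Day 1".

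Section 8.43, which governs second and later doses of the antibody and irinotecan, says: "If any of the events listed below occurs after the previous dose, the next dose will be reduced or discontinued". The first row of table 8.432 gives a one-level irinotecan reduction for grade 4 neutropenia or thrombocytopenia. The next row reads "Grade 3 neutropenia or grade 3 thrombocytopenia for more than 7 days". Its action cell is empty in the machine-read text, and I take it as merged with the cell above.

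Section 8.0 sets the status of the tables: "Strictly follow the modifications in the following tables for the first" two cycles. After that: "Thereafter, these modifications should be regarded as guidelines to produce mild-to-moderate, but not debilitating, side effects". Section 7.0 adds: "The use of irinotecan is per treating physician discretion and will be dosed per prescribing guidelines".

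**The concern.** For one patient with one event, two current sections give two different irinotecan doses, and nothing says which prevails. Section 8.5 carries the title for neutropenia, leukopenia and thrombocytopenia, so a clinician managing such an event would naturally turn there. It does not send the reader on to 8.432.

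The stake is patient safety. A site relying on 8.5 could give again the irinotecan dose that preceded grade 4 myelosuppression. Section 15.47 of the protocol itself notes a boxed warning for severe myelosuppression with this drug.

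**Working it through.** The plan states no figure on this point. The check is a comparison of the rules, followed by simple arithmetic.

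**1. The two rules for irinotecan, by event**

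| Event, once recovered to grade 1 or less | Section 8.5 | Sections 8.43 and 8.432 |
|---|---|---|
| Grade 4 neutropenia or thrombocytopenia | Same dose permitted | One level down |
| Grade 3 neutropenia or thrombocytopenia beyond 7 days | Same dose permitted | One level down, if the empty cell is merged |
| Grade 3 neutropenia or thrombocytopenia of 7 days or less | Same dose permitted | Not listed, so no conflict |
| Grade 3 or 4 leukopenia | Same dose permitted | Not listed, so no conflict |

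Table 8.431 has no cytopenia row, so there is no conflict for cetuximab or panitumumab either. Section 8.5 grants a permission and 8.43 is worded as a requirement. Reducing the dose satisfies both sections; repeating it satisfies only 8.5.

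**2. Which rule governs, and when**

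- Cycles 1 and 2: 8.0 makes the tables strict, which favours 8.432.
- Cycle 3 onwards: 8.0 makes the tables guidelines, while 8.5 has no cycle limit. A guideline to reduce then meets an express permission not to.

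**3. Size of the dose difference**

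Table 7.22 gives irinotecan levels of 180, 150 and 120 mg/m².

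- From the initial level: 180 / 150 = 1.20, so 8.5 allows a dose 20% higher.
- From level -1: 150 / 120 = 1.25, so 25% higher.

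**4. How much of treatment 8.0 leaves unsettled (illustration)**

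Section 7.1 schedules irinotecan on days 1 and 15 of 28, that is, every 14 days. Cycles 1 and 2 hold doses on days 1, 15, 29 and 43: 4 doses, of which 3 are second or later.

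Section 1.1 cites median progression-free survival of 4.1 and 4.0 months in two studies of cetuximab plus irinotecan. At 30.44 days per month:

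- 4.1 × 30.44 = 124.8 days and 4.0 × 30.44 = 121.8 days. In both cases the last planned dose is on day 1 + 8 × 14 = 113, so 9 doses are planned.
- 9 − 4 = 5 doses come after cycle 2. Of the 8 second and later doses, 3 are in the strict period and 5 after it (5 / 8 = 62.5%).
- For an assumed 3 months: 3 × 30.44 = 91.3 days, last dose on day 85, 7 doses planned. 7 − 4 = 3 come after cycle 2, so the 6 second and later doses split 3 and 3 (50%).

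These counts assume no delays and irinotecan continued to progression. They show that the unsettled period is not marginal; they do not measure risk.

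**The case against.** The best reply is that the sections can be read together. Section 8.0 settles the first two cycles. After that it already lets the physician depart from the table, so the permission in 8.5 adds little. If the prose of 8.43 stays binding because it is not a table, a specific irinotecan rule would ordinarily prevail over a general one. The last sentence of 8.5 still has work to do where 8.432 is silent, for example on leukopenia, short grade 3 cytopenia and the antibodies. Restart under 8.5 also requires recovery to grade 1 or less, 8.42 sets minimum counts for irinotecan, and 7.0 refers to prescribing guidelines.

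Much of this is fair. A site that always reduces breaches neither section, and cycles 1 and 2 are largely protected. The grade 3 row depends on how an empty cell is read, so grade 4 carries the point. The dose counts rest on planned schedules, although the affected patients are by definition interrupted, and the 4.0-month figure comes from a second-line study.

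It does not remove the conflict. The protocol states no rule that the specific section prevails. Recovery and start counts decide when irinotecan may resume, not at what dose. The prescribing guidelines are not reproduced, so what they would require cannot be judged. Discretion to depart from a guideline is also weaker than a sentence that expressly permits the same dose.

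One further objection deserves an answer: editing 8.5 alone leaves 8.0 as it is. The amendment should therefore say whether 8.432 sets the restart dose in every cycle.

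**Conclusion.** The concern holds. For recovered grade 4 neutropenia or thrombocytopenia, 8.5 permits an irinotecan dose 20% or 25% above the one in 8.432, with no cross-reference and no order of precedence. The conflict is clearest from cycle 3. It extends to grade 3 events beyond 7 days only if the empty cell in 8.432 is merged with the one above.

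The number of patients affected is unknown: the documents give neither a grade 3 or 4 cytopenia rate for this population nor the expected share receiving irinotecan. This is a safety inconsistency that should be corrected. It has no claimed effect on the overall survival comparison.

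**What to change.** Add to the end of 8.5: *Restart at the same dose does not apply to irinotecan after an event listed in 8.432; in that case 8.432 sets the restart dose.* Add the words *in all cycles* if that is the intention. I would include them, while acknowledging openly that this tightens 8.0 for this event. Keep the recovery requirement in 8.5 alongside the irinotecan start counts in 8.42.

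As a side note only, 8.5 could also point to table 8.21 for regorafenib where footnote b of that table does not exempt the event.

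The cost is one sentence in the next amendment, with no change to sample size, visits or analysis.
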